3.6 By-Site Analyses

Only one site will be included in this study, so there will be no specific “by site” analyses.

3.7 Descriptive Statistics on Differences (D) and Relative Differences (RD) from Reference

Descriptive statistics: mean (average), standard deviation, median, minimum, and maximum of D ($\text{LabBG} < 100 \text{ mg/dL}$) and RD ($\text{LabBG} \geq 100 \text{ mg/dL}$), will be computed.

3.8 Confidence Intervals

Confidence intervals (95%, two-sided) for all ISO and FDA objective proportions (percents) will be computed using the Clopper-Pearson¹ (1934) formula:

$$P_L = \frac{X * F_{\alpha/2}^{-1}(2X, 2(n - X + 1))}{n - X + 1 + X * F_{\alpha/2}^{-1}(2X, 2(n - X + 1))}$$

¹ Clopper, C.J., Pearson, E.S. (1934) The use of confidence or fiducial limits as illustrated in the case of the binomial, *Biometrika*, 26, 404-413

and:

$$P_U = \frac{X * F_{1-\alpha/2}^{-1}(2X, 2(n - X + 1))}{n - X + 1 + X * F_{1-\alpha/2}^{-1}(2X, 2(n - X + 1))}$$

P_L = lower limit

P_U = upper limit

X = number of “accurate” results (per the relevant definition of “accurate”)

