1.3 Internal Objective

For subjects with diabetes only (PWDs):

The criterion is defined to be:

$|D| \leq 12.5 \text{ mg/dL}$ if $\text{LabBG} < 100\text{mg/dL}$, or:

$|RD| \leq 12.5\%$ if $\text{LabBG} \geq 100\text{mg/dL}$

The hypothesis:

$$H_0: \Pr\{\text{criterion met}\} < 95\%$$

will be tested against the alternative:

$$H_1: \Pr\{\text{criterion met}\} \geq 95\%$$

With $n = 315$, the critical value is $X_c = 294$ yields a power to reject H_0 if $\Pr\{\text{criterion met}\} = 0.95$ is $\sim 92.63\%$.

Table 1.1 summarizes the power statements made in 1.1, 1.2, and 1.3.

Table 1.1 Power Statements for ISO and FDA Acceptance Criteria

Criterion	N	Xc	Po*	Pr{PASS Po}	Pa**	Pr{FAIL Pa}	
ISO	315	300	96.79%	95.02%	92.77%	94.95%	
±12.5	315	294	95.00%	92.63%	90.60%	94.64%	
FDA-15%	350	333	96.65%	95.00%	92.81%	94.95%	
FDA-20%	350	347	99.61%	95.05%	97.80%	95.00%	

*Po is the minimum required (hypothetical) probability that any measurement would meet the definition of an "accurate" result, in order to have approximately a 95% chance that at least Xc out of N results would be "accurate" (PASS)

**Pa is the maximum required (hypothetical) probability that any measurement would meet the definition of an "accurate" result, in order to have approximately a 95% chance that fewer than Xc out of N results would be "accurate" (FAIL)

In general, critical values depend on actual sample size. The sample size and associated critical values for accuracy tests (the minimum required numbers of "accurate" results) are determined by regulatory guidance. The values of Po and Pa are affected by actual sample size.

2. Blood Glucose Measurements

Some data analysis follows analyses and presentations described in ISO Section 15197:2013, Section 8. See Table 3 for scheme of data analysis, including capillary blood and venous blood.

Other data analysis follows analyses and presentations described in the FDA 2018 OTC Guidance. See Table 4 for scheme of FDA 2018 OTC data analysis, including capillary blood and venous blood.

Blood glucose measurements will all be made in units of mg/dL. Graphs (other than error grids) involving blood glucose concentrations will be constructed in both mg/dL and mmol/L (for ISO analyses; analyses for FDA reporting will include tables and graphs in mg/dL only). The conversion of $X \text{ mg/dL}$ to $Y \text{ mmol/L}$ will be as follows:

$$Y \text{ mmol/L} = \frac{X \text{ mg/dL}}{18.016}$$

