3.3 FDA Objectives

3.3.1 95% within $\pm 15\%$

With $n = 350$, at least $X_c = 333$ measurements must be within $\pm 15\%$ of LabBG. This requirement is equivalent to testing the hypothesis:

$$H_0: \Pr\{|RD| \leq 15\% \} < 0.9664$$

against the hypothesis:

$$H_1: \Pr\{|RD| \leq 15\% \} \geq 0.9664$$

with $\Pr\{\text{reject } H_0 | p=0.9664\} \approx 0.9488$

3.3.2 99% within $\pm 20\%$

With $n = 350$, at least $X_c = 347$ measurements must be within $\pm 20\%$ of LabBG. This requirement is equivalent to testing the hypothesis:

$$H_0: \Pr\{|RD| \leq 20\% \} < 0.9960$$

against the hypothesis:

$$H_1: \Pr\{|RD| \leq 20\% \} \geq 0.9960$$

with $\Pr\{\text{reject } H_0 | p=0.9960\} \approx 0.9466$

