3.5 Some Additional Comments about Hypothesis Tests

Power and risk calculations were made based on the assumption that $n = 315$ for the ISO accuracy objective, and for $n = 350$ for the FDA accuracy objective. It is possible that the total number of results may differ from the minimum requirement, depending on the numbers of subjects actually enrolled and the number of evaluable results. The critical value is always 95% of the total sample size of evaluable results. However, power statements made earlier were based on $n = 315$ or $n = 350$, so these statements may only be approximate.

No adjustment will be made for multiplicity. Each test will be evaluated without regard to the results of any other test.

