Runs using serum control material at multiple levels will be executed daily for each laboratory glucose comparator instrument used in the study. The run means will be compared to lower and upper limits for each level. If the minimum and maximum value of individual measurements are within lower and upper limits, the run means do not need to be compared to those limits also.

A regression line will be fit using the instrument results regressed against target values as set by Ascensia Diabetes Care analytical laboratory. For levels with target values below 75 mg/dL, the within-run and between standard deviation (SD) will be computed; for levels with targets great than or equal to 75 mg/dL, the coefficient of variation (CV) will be computed, using the average over all runs.

Scatterplots of control result against targets, together with regression lines, for each instrument will be constructed. The Differences from target will be plotted against the target values for each instrument.

13. Meter Control Solution Results

Each meter unit used in the study will have control solution tests performed. The acceptable range of control solution results is specific to each meter, and the limits are provided by R&D or Quality Assurance. The control solution results must fall within prescribed limits in order for a meter to be used in the study. There are up to 3 attempts allowed to obtain a within-limit result for each meter.

Mock Tables and Graphs

Mock tables and graphs are intended to illustrate the general nature of such tables and graphs that are to be included in the study report. As such, they are facsimiles; actual tables and graphs may vary from the mock versions. For example, studies may have more than one site. The actual tables indicating results are computed by site would have results for each site included in the study.

Section 3 – Proportions: Applies to Sections 3.1-3.3, 3.5, 3.7

Table 3.1. Proportion $-15 \text{ mg/dL} \leq D \leq +15 \text{ mg/dL}$ (LabBG < 100 mg/dL) or $-15\% \leq RD \leq +15\%$ (LabBG $\geq 100 \text{ mg/dL}$)

Level	Count	Percent	Lower CI	Upper CI	1-Alpha
In	317	97.84%	95.61%	98.95%	0.95
Out	7	2.16%	1.05%	4.39%	0.95
Total	324				

Section 3 – Descriptive Statistics for D, RD

[figure not shown]
Table 3.2. Descriptive Statistics for D and RD

Level mg/dL	Variable	N	Mean	Std Dev	Min	Max	Median
LT 100	D (mg/dL)	74	2.19	4.470	-12.40	15.20	2.75
GE 100	RD (%)	297	3.17	4.945	-28.09	25.36	3.23

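### SAP 3.8 names Clopper-Pearson but prints the upper limit with the lower limit's terms, so every upper limit coded from it is too low

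*SAP*

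**What the plan says.** SAP 3.8 fixes the interval method for the accuracy results: "Confidence intervals (95%, two-sided) for all ISO and FDA objective proportions (percents) will be computed using the Clopper-Pearson" formula, with the 1934 paper cited. X is the number of accurate results among n. In plain notation the two limits are printed as:

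- P_L = X·F / (n-X+1 + X·F), with F the alpha/2 quantile of the F distribution on 2X and 2(n-X+1) degrees of freedom.
- P_U = X·F / (n-X+1 + X·F), with F the 1-alpha/2 quantile on the same 2X and 2(n-X+1) degrees of freedom.

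No convention is given for X = 0 or X = n. No other section of the SAP or protocol restates or corrects the formula.

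Acceptance does not use these limits. SAP 1.1, 1.2 and 3.3 set minimum counts of 300/315 (ISO), 333/350 (FDA 15%) and 347/350 (FDA 20%). SAP 3.5 adds: "The critical value is always 95% of the total sample size of evaluable results".

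The only interval for an accuracy proportion shown in the documents is in mock Table 3.1: 317/324, 95.61% to 98.95%. The SAP says of its mock tables that "they are facsimiles; actual tables and graphs may vary from the mock versions".

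**The concern.** The two Clopper-Pearson limits come from different tail probabilities, so they need different degrees of freedom. A formula in which only the quantile changes cannot give both. The lower limit is the one printed correctly, so the error falls on the upper limit.

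At stake are the reported intervals for all ISO and FDA objective proportions, in two clinical study reports (protocol 9.8). If the formula is coded as printed, the reports will label as Clopper-Pearson an interval that is not one and that lacks the coverage guarantee for which the method is chosen. If a library routine is used instead, the output will be right, but anyone re-deriving it from SAP 3.8 will get different upper limits.

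**Working it through.** **Inputs.** alpha = 0.05 and both formulas from SAP 3.8; n and critical counts from SAP 1.1, 1.2 and 3.3; Pa and P0 from SAP Table 1.1; the 0.9960 boundary from SAP 3.3.2; 317/324 from mock Table 3.1.

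**The plan's own figures.** The binomial probabilities in Table 1.1 reproduce: Pr{PASS} 95.02%, 92.63%, 95.00%, 95.05%; Pr{FAIL} 94.95%, 94.64%, 94.95%, 95.00%. None of them uses P_U. The mock interval does not reproduce from SAP 3.8. For 317/324:

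| Method | Lower | Upper |
|---|---|---|
| Mock Table 3.1 | 95.61% | 98.95% |
| SAP 3.8 as printed | 95.60% | 98.93% |
| Exact Clopper-Pearson | 95.60% | 99.13% |
| Wilson score | 95.61% | 98.95% |

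The mock row is a Wilson interval, so it cannot show which P_U was intended.

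**Algebra.** If F has 2a and 2b degrees of freedom, aF/(b+aF) has a Beta(a, b) distribution. Hence:

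- Printed P_L is the 0.025 quantile of Beta(X, n-X+1), which is the exact lower limit.
- Printed P_U is the 0.975 quantile of Beta(X, n-X+1).
- The exact P_U is the 0.975 quantile of Beta(X+1, n-X), with P_U = 1 at X = n.

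Putting X-1 for X in the exact form gives Beta(X, n-X+1). So printed P_U at X equals exact P_U at X-1. Numerically the two agree to about 1e-16 for every X at n = 315, 324 and 350. Reading F as an upper-tail quantile does not help, because the two limits would only swap.

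**Example, 300/315.**

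- Printed: F(0.975; 600, 32) = 1.7664, so P_U = 300×1.7664 / (16 + 300×1.7664) = 529.92/545.92 = 97.07%.
- Exact: F(0.975; 602, 30) = 1.8032, so P_U = 301×1.8032 / (15 + 301×1.8032) = 542.76/557.76 = 97.31%.

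**Upper limits** (shortfalls in percentage points, from unrounded values):

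| X/n | Printed P_U | Exact P_U | Shortfall |
|---|---|---|---|
| 300/315 | 97.07% | 97.31% | 0.24 |
| 333/350 | 96.92% | 97.15% | 0.22 |
| 346/350 | 99.53% | 99.69% | 0.15 |
| 347/350 | 99.69% | 99.82% | 0.14 |
| 350/350 | 99.993% | 100% | 0.007 |

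Over all X the shortfall runs from about 0.007 to 0.59 points. At X = n the printed limit lies below the observed 100%.

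**Coverage.** Coverage is the sum of binomial probabilities over those X whose interval contains p. On a fine grid over each Pa-P0 range:

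| Criterion | p range | Printed, lowest (at p) | Printed, average | Exact, lowest |
|---|---|---|---|---|
| ISO, n = 315 | 0.9277-0.9679 | 93.1% (0.9633) | 94.97% | 95.0% |
| FDA 15%, n = 350 | 0.9281-0.9665 | 93.5% (0.9625) | 94.98% | 95.3% |
| FDA 20%, n = 350 | 0.9780-0.9961 | 91.8% (0.9953) | 95.08% | 95.9% |

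The probability that the printed upper limit falls below p exceeds 2.5% at every grid point in all three ranges. For the exact limit it never does.

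**At the SAP 3.3.2 boundary** (p = 0.9960, n = 350), the printed interval lies wholly below p when X ≤ 346. That has probability 1 - 0.9466 = 5.34%, the complement of the SAP's own figure. The exact interval misses only when X ≤ 345, with probability 1.40%. Neither misses on the other side, since P_L is at most 98.95%. Coverage is therefore 94.66% printed and 98.60% exact.

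**The case against.** The strongest reply is that nothing in the plan depends on P_U. Acceptance is by count, and the lower limit, which bears on a claim of at least 95% or 99%, is exact. The shift at the critical counts is at most 0.24 points. Average coverage of the printed interval is about 95%, so the minima in the table should not be read as general under-coverage. At 346/350 the printed interval excludes 0.9960 and the exact one does not, but 346 already fails by count, no section compares a confidence limit with 0.9960, and both intervals contain 99%. A Wilson interval would also lack guaranteed coverage: at p = 0.9960 its coverage is likewise 94.66%, and its upper limit at 346/350 is 99.55%. Finally, a programmer who follows the named method may never code the printed formula.

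All of this is true, and it limits the weight of the point. The coverage figures do not make the printed interval useless; they show that it lacks the property of the method it is named for. They do not remove the mismatch between formula and method, the upper-side miss above 2.5% throughout the planning ranges, or the interval that excludes its own estimate at X = n, which Wilson does not do. The mock table is declared a facsimile and counts only as a consistency remark.

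**Conclusion.** The point holds. The printed P_U is the exact upper limit for one fewer success and is too low for every X: by 0.14 to 0.24 percentage points at the three ISO and FDA critical counts, and by up to about 0.59 points over all X. Within the Table 1.1 ranges coverage can fall to 91.8%-93.5%, where the exact interval stays at or above 95.0%. The lower limit, critical counts, power statements and every pass/fail outcome are unaffected.

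The effect on reported results assumes that the formula is programmed as printed, which the documents do not settle. Coverage was computed with independent binomial results at the planned n of 315 and 350. This is a definite error in a pre-specified method with small numerical consequences, and it should be corrected before the reports are produced.

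**What to change.** In SAP 3.8, replace the upper limit by P_U = (X+1)·F / [n-X + (X+1)·F], with F the 1-alpha/2 quantile on 2(X+1) and 2(n-X) degrees of freedom. State P_U = 1 when X = n and P_L = 0 when X = 0. Leave P_L as it is.

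Check the analysis program against known values: 300/315 gives 92.27% to 97.31%, 347/350 gives 97.52% to 99.82%, and 350/350 gives 98.95% to 100%.

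For consistency, show mock Table 3.1 with exact limits: 95.60% to 99.13% for the accurate row and 0.87% to 4.40% for its complement. Naming Wilson throughout would also make text and mock agree, but it would give up guaranteed coverage, so correcting the formula is the better course.

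The cost is one formula, one mock table and a program check. No data, sample size or critical value changes.

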3.9 Error Distributions

The numbers and percents of values of D (LabBG < 100 mg/dL) falling within ± 5 , ± 10 , ± 15 , and ± 20 mg/dL, and the numbers and percents of values of RD (LabBG ≥ 100 mg/dL) falling within ± 5 , ± 10 , ± 15 , and ± 20 percent will be tabulated.

4. Regression, Modified Bland-Altman Plots, Radar Plot, and Outlier Analysis

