1.2 FDA Objective – Accuracy with All Subjects Included

For the FDA accuracy objective, a result (MeterBG) is considered accurate if:

$$|RD| = 100 * |\text{MeterBG} - \text{LabBG}| / \text{LabBG} \leq 15\%, \text{ regardless of the value of LabBG.}$$

Assuming $n = 350$ evaluable results, $X_c = 333$ results would be required to satisfy the accuracy criteria. At $P_0 = 96.65\%$, there is approximately a 95% chance of satisfying the FDA 15% objective. Conversely, at $P_a = 92.81\%$, there is approximately a 95% chance of failing to satisfy the FDA accuracy objective.

The FDA guidance has a second criterion, that 99% of n evaluable results must have $|RD| \leq 20\%$. Inasmuch as the two criteria are considered separately, there is no consideration for multiplicity. For the $n = 350$, the 20% criterion requires a critical value of $X_c = .99 * 350$

$= 346.5 \rightarrow 347$. For this critical value and sample size, with $P_0 = 99.61\%$, there is approximately a 95% chance of satisfying the FDA 20% criterion. Conversely, there is approximately a 95% chance of failing to satisfy the 20% criterion if the chance of obtaining a result within $\pm 20\%$ of corresponding comparator measurement is only 97.8%.

Note that each glucose result obtained with the evaluation device will be considered either 'accurate' or 'not accurate', where accuracy depends on the particular test criterion.

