3.1 ISO Objective

At least 95% of the glucose results obtained using the evaluation device must be accurate, namely:

$$-15\% \leq RD \leq +15\% \quad \text{LabBG} \geq 100\text{mg/dL}$$

OR

$$-15\text{mg/dL} \leq D \leq +15\text{mg/dL} \quad \text{LabBG} < 100\text{mg/dL}$$

As discussed in section 0 (Sample Size), with $n = 315$, the critical number (minimum) of accurate results is 300, which yields approximately a 95% chance of satisfying the ISO objective criterion if the actual probability that any result will be accurate is at least 96.79%. Symbolically, the ISO criterion is equivalent to testing the hypothesis:

$$H_0 : \text{Prob}\{\text{accurate}\} < 96.79\%$$

versus the alternative:

$$H_1 : \text{Prob}\{\text{accurate}\} \geq 96.79\%$$

There is approximately a 95% chance that the null will NOT be rejected if the actual probability that a result with the evaluation device would satisfy this definition of accuracy is only about 92.76%.

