2.2.4 Fingerstick Test: Obtain T-PLUS BGMS performance data in the hands of **lay users with diabetes and naïve users** (without diabetes) from fingerstick capillary blood using Microlet NEXT lancing device.

- **95% of glucose results shall fall within $\pm 15\%$ of laboratory method across the entire tested range**
- **99% of glucose results shall fall within $\pm 20\%$ of laboratory method across the entire tested range**

2.2.5 Alternative Site Test (AST): Obtain T-PLUS BGMS performance data in the hands of **lay users with diabetes and naïve users** (without diabetes) from the palm site using the Microlet NEXT lancing device with the AST endcap. Acceptance criteria will be the same as fingerstick 2.2.4.

2.2.6 Samples will adequately span the claimed measuring range. At least ten unaltered samples with blood glucose concentration at the lower limits of the measuring range (less than 80 mg/dl) and at least ten unaltered samples at the upper limit measuring range (greater than 250 mg/dl) will be obtained for each anatomical site (i.e. fingerstick & palm).

2.2.7 Subject Questionnaire 1: The questionnaire will include statements about the T-PLUS BGMS instructions for use (product labeling) and ease of use of the basic blood testing operations of the meter system. These statements will be given a rating by all of the subjects (1=strongly disagree, 2=disagree, 3=neutral, 4=agree, 5=strongly agree), and frequency distributions will be tabulated. Results will be compared to the following criteria:

- **Acceptance criteria **: There will be no pass/fail criteria for FDA: SMBG 2018**

*This is a “total population” (hypothesis test) requirement for the pool of all subjects with diabetes.

** This is a “total population” (hypothesis test) requirement for the pool of all subjects (naïve and diabetic).

Study objectives 2.2.8 to 2.2.10 below are internal objectives and apply to data collected from all subjects OR subjects who have diabetes, as specified for each objective.

2.2.8 **Fingerstick Test (only subjects with diabetes):** Obtain T-PLUS BGMS performance data in the hands of lay users with diabetes using fingerstick capillary blood obtained with Microlet NEXT lancing device.

- **Test the hypothesis that there is at least a 95% probability that meter results would be within $\pm 12.5\text{mg/dL}$ of laboratory method at glucose concentrations $<100\text{ mg/dL}$ and within $\pm 12.5\%$ at glucose concentrations $\geq 100\text{ mg/dL}^{**}$**

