3.0 Study Design Summary

This study is designed to satisfy both the ***FDA SMBG:2018*** and the ***ISO 15197:2013, Section 8*** requirements. Besides different analysis criteria, the main difference between these regulations is that FDA SMBG:2018 requires that both naïve users (people without diabetes) and people with diabetes to be included in the study population. The ISO 15197:2013 standard states that the study population shall only include people with diabetes.

The study will be conducted at minimum of one clinical site and enroll a total of approximately 370 lay users. Ten to fifteen percent (10 - 15%) of the enrolled subjects will be people without diabetes and twenty percent (20%) of subjects enrolled with diabetes will have Type 1 diabetes. At least 70% of subjects will be younger than age 65.

For this study, there must be at least 350 total evaluable fingerstick self-test results and at least 350 total evaluable AST palm self-test results. ISO 15197:2013 criteria requires at least 100 evaluable results each for fingerstick self-test results, AST palm self-test results, study staff performed fingerstick blood and venous blood tests.

In addition, per FDA SMBG:2018, at least 10 unaltered evaluable subject fingerstick and AST palm blood samples will be $< 80\text{ mg/dL}$ and 10 will be $> 250\text{ mg/dL}$ (by capillary YSI assay). Subject enrollment will continue until the required evaluable samples are collected.

The subjects will be 18 years and older. Each subject will make one visit, lasting approximately 1 hour at the clinical site. Study sessions will be conducted by study staff members who have been trained on all aspects of the protocol, the use of the T-PLUS system, data collection, and GCP.

Procedures: All subjects will complete the informed consent process before performing any study procedures.

- **For All Subjects**

Subjects will be assigned to use the T-PLUS meter and randomized to use one of three Contour Plus test strip lots throughout the visit.

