4.3 Subject Recruitment

4.3.1 The following additional population criteria are study goals with the site recruiting to meet these goals:

1. Enrolment: At least 370 subjects
2. At least 70% of subjects will be younger than age 65.
3. Ten to fifteen % (10-15%) of subjects will be people without diabetes.
4. At least 20% of subjects (with diabetes) will have type 1 diabetes.

4.3.2 There must be at least 350 total evaluable fingerstick self-test results and at least 350 total evaluable AST palm self-test results. ISO 15197:2013 criteria requires at least 100 evaluable results each for fingerstick self-test results, AST palm self-test results, study staff performed fingerstick blood and venous blood tests.

4.3.3 In Addition, per FDA SMBG:2018, at least 10 unaltered evaluable subject fingerstick and AST palm blood samples will be < 80 mg/dL and 10 will be > 250 mg/dL (by capillary YSI assay). Subject enrollment will continue until the required evaluable samples are collected

4.3.4 No laboratory tests (e.g., pregnancy) are required to assure qualification. Subjects' verbal responses will be accepted and recorded on forms which will serve as source documents for the electronic data capture (EDC) system.

4.3.5 The site study staff will perform the following when the subject arrives at the clinical trial site:

1. Complete the informed consent process.
2. Assign a unique number to each subject.

4.3.6 The study staff will document subject demographics (including both screen-failed and enrolled subjects), diabetes history, medical conditions and medications information. Subjects will also be asked when they last ate, took diabetes medications, and performed vigorous exercise.

4.3.7 If the subject does not have diabetes, the outside of the subject folder will be labeled to indicate that venipuncture should NOT be performed.

4.3.8 According to the randomization schedule, subjects will be assigned to use one of three Contour Plus test strip lots (R,B or G) throughout the visit.

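### Enrolment continues until samples below 80 and above 250 mg/dL are obtained, but no planned summary gives an accuracy rate in either range

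*SAP*

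**What the plan says.** Protocol 2.2.4 sets the FDA fingerstick criteria: "95% of glucose results shall fall within $\pm 15\%$ of laboratory method across the entire tested range", and 99% within ±20% over the same range. Protocol 2.2.5 applies them to palm tests. Protocol 2.2.6 adds that "Samples will adequately span the claimed measuring range". Protocol 4.3.3 makes this concrete: "at least 10 unaltered evaluable subject fingerstick and AST palm blood samples will be < 80 mg/dL and 10 will be > 250 mg/dL". Protocol 3.0 ties recruitment to it: "Subject enrollment will continue until the required evaluable samples are collected".

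The SAP uses these two ranges in one place. Section 9.3 reports the number of capillary samples in each, and mock Table 9.1 shows counts only. Elsewhere:

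- SAP 3.7 (descriptive statistics) and SAP 3.9 (error distributions) split at 100 mg/dL only. Section 3.9 covers "The numbers and percents of values of D (LabBG < 100 mg/dL) falling within" mg/dL limits, and relative differences at 100 mg/dL or more.
- Table 6.1 (ISO) and Table 6.2 (FDA, in percent) name no glucose strata.
- Every pass rule pools all evaluable results. For ISO, SAP 3.1 states that "the critical number (minimum) of accurate results is 300" of 315. SAP 1.2 requires 333 of 350 for FDA ±15% and 347 of 350 for FDA ±20%.

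**The concern.** The trial may prolong enrolment to obtain samples at both ends of the range, and its FDA criteria refer to the whole range. Yet no table says what proportion of the results at those ends was accurate. Samples below 80 are merged with those from 80 to 99, and everything from 100 mg/dL up forms one group. The pooled rules do not fill the gap, because the required number of low samples is smaller than the number of misses each 95% rule tolerates. A report could state that a 95% criterion was met over the tested range without giving the reader a low-end or high-end figure to set beside that statement.

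**Working it through.** **Inputs.** Critical values and operating characteristics are from SAP Table 1.1. The minimum tail counts (10 below 80, 10 above 250) are from Protocol 2.2.6 and 4.3.3.

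**1. Reproduce the plan's figures.** With X binomial(n, p), Pr(pass) = Pr(X ≥ Xc).

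| Rule | n | Xc | Pr(pass) at P0, plan / recomputed | Pr(fail) at Pa, plan / recomputed |
|---|---|---|---|---|
| ISO | 315 | 300 | 95.02% / 0.9502 | 94.95% / 0.9495 |
| FDA ±15% | 350 | 333 | 95.00% / 0.9500 | 94.95% / 0.9495 |
| FDA ±20% | 350 | 347 | 95.05% / 0.9505 | 95.00% / 0.9500 |

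The table reproduces.

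**2. Misses allowed = n − Xc.** ISO 315 − 300 = 15; FDA ±15% 350 − 333 = 17; FDA ±20% 350 − 347 = 3.

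**3. All 10 low samples miss, each 95% rule taken alone.**

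- ISO: 305/315 = 96.83%. This passes with 15 − 10 = 5 misses to spare, assuming all 10 come from people with diabetes.
- FDA ±15%: 340/350 = 97.14%. This passes with 17 − 10 = 7 misses to spare.
- If all 10 high samples also missed, the 20 misses would exceed both 15 and 17, and both rules would fail.

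**4. How good the rest must be.** Pr(pass) is Pr(Bin(305, p) ≥ 300) for ISO and Pr(Bin(340, p) ≥ 333) for FDA ±15%, where p is the accuracy outside the low range. The values of p are assumptions.

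| p elsewhere | ISO | FDA ±15% |
|---|---|---|
| 98% | 0.428 | 0.629 |
| 99% | 0.912 | 0.978 |
| 99.5% | 0.995 | >0.999 |

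**5. Both FDA criteria together.** At most 3 results may exceed ±20%. If all 10 low samples miss ±15% and both criteria pass, at least 10 − 3 = 7 of them must be more than 15% but no more than 20% off.

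**6. Low ISO misses against the ±20% rule.** Below 100 mg/dL an ISO miss is an error over 15 mg/dL. At LabBG 75, 15/75 = 20%, so every ISO miss below 75 also exceeds ±20%. Between 75 and 80, 20% of LabBG is 15 to 16 mg/dL, so only errors in that 1 mg/dL band can miss ISO and stay within ±20%.

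**7. More than 10 low samples.** With 22 (the illustrative count in mock Table 9.1) at the same n and Xc, low-range accuracy could be as low as (22 − 15)/22 = 31.8% for ISO or (22 − 17)/22 = 22.7% for FDA ±15%, each rule again taken alone.

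**8. What 10 samples can show.** Exact two-sided 95% Clopper-Pearson limits: 10/10 gives 69.2-100%, 7/10 gives 34.8-93.3%, 0/10 gives 0-30.8%.

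**The case against.** Much of the opposing case stands.

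- **The ±20% rule.** A reader might infer that the FDA objective could be met with the low end grossly wrong. Steps 5 and 6 rule that out: at most 3 results can be more than 20% off. The ISO subjects are a subset of the FDA set, so most low ISO misses would count against the ±20% rule too.
- **Visibility.** A reader might infer that poor tail accuracy would go unseen. It would not. SAP 4.2 plots differences against LabBG over the full range with the ISO limits drawn. Scatter plots, radar plots and error grids are also planned, results beyond ±20% are listed (note to Table 6.2), and SAP 10 lists the individual meter and YSI results. A rate could be worked out from these, but no output states one, and the ±20% list omits results 15% to 20% off.
- **The mg/dL scale in SAP 3.9.** A reader might infer that this scale conceals percent errors at low glucose in the FDA analysis. It does not, because Table 6.2 already tabulates FDA errors in percent; that table only lacks strata.
- **Purpose.** Protocol 2.2.6 gives the aim of the tail samples as spanning the range, which a count does verify. The documents do not say that they were recruited to estimate accuracy in subgroups, so the plan does not fail a stated aim.
- **Size of the tails.** The minimum of 10 per tail is a floor, not an expected count. Mock Table 9.1 shows 22 and 31 of 375, or 53/375 = 14.1%, and is itself only illustrative.
- **Yield and authority.** Intervals from 10 samples are wide, and the SAP says regulatory guidance sets the critical values. Both argue against a tail-specific pass mark. Neither argues against a descriptive table.

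**Conclusion.** The point holds as a reporting gap. Neither document plans an accuracy percentage, with or without an interval, for LabBG below 80 or above 250 mg/dL, although enrolment depends on obtaining those samples and the FDA criteria are worded for the whole tested range.

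The arithmetic is a worst-case bound on what the pooled rules permit, not a prediction of how this meter performs. It rests on the minimum of 10 low samples, on n = 315 and n = 350, on each 95% rule being taken alone and, for ISO, on all 10 low samples coming from people with diabetes. On those terms low-end accuracy could be 0 of 10 and either 95% rule could still pass, provided accuracy elsewhere is high (step 4). With both FDA criteria applied, such a result is confined mainly to errors between 15% and 20%.

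The documents do not support the wider conclusions that the acceptance criteria are wrong or that tail results would be concealed. The change is worth making because it is cheap and lets the report state accuracy at the ends of the range.

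**What to change.** Add to SAP 3.9, and reference in Tables 6.1 and 6.2, one descriptive table giving n and the number and percent of results within each planned limit for LabBG <80, 80-250 and >250 mg/dL. Use percent limits for the FDA set, and mg/dL or percent according to LabBG for the ISO set. Produce it for each capillary test type: subject fingerstick, staff fingerstick and palm. Palm results need their own row, because Tables 6.1 and 6.2 list only subject and staff capillary results while Protocol 2.2.6 sets the tail counts for finger and palm.

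Attach standard exact Clopper-Pearson 95% intervals. The upper limit printed in SAP 3.8 reuses the degrees of freedom of the lower limit; for 7/10 it gives 87.8% instead of 93.3%, so the standard form should be programmed.

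Leave all pass marks unchanged, and state that any claim about the entire tested range is to be read together with this table. Specify it before results are seen.

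The cost is one more table from data already collected. The downside is wide tail intervals at the minimum counts: 10/10 gives 69-100% and 0/10 gives 0-31%. The table can show a gross failure at one end but cannot establish good accuracy there.
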